6.1. Analysis of Patients

6.1.1. Patient Composition Diagram

- 1) Analysis set Enrolled patients
- 2) Chart plan Figure 1-1
- 3) Analysis items
 - Number of registration sites
 - Number of enrolled patients
 - Number of patients with no CRF collected (including reasons for collecting no CRF)
 - Number of patients with the CRF collected
 - Number of patients not evaluated for safety (including reasons for exclusion)
 - Number of patients evaluated for safety
 - Number of patients not evaluated for efficacy (including reasons for exclusion)
 - Number of patients evaluated for efficacy
 - Number of patients not evaluated for vertebral fracture (including reasons for exclusion)
 - Number of patients evaluated for vertebral fracture
- 4) Analysis methods The number of patients (number of sites) will be calculated for the analysis item, and a composition diagram will be prepared.

6.1.2. Patient Baseline Characteristics

| | |
|-------------------|--|
| 1) Analysis set | Patients evaluated for safety |
| | Patients evaluated for vertebral fracture |
| 2) Chart plan | Table 1-2 |
| 3) Analysis items | 
Sex [male, female, unknown]
 
Age (years)^{*1} [<65 years, ≥65 years, unknown], [<75 years, ≥75 years, unknown]
 
Height before the start of treatment (cm)^{*1}
 
Body weight (kg)^{*1} [<50.0 kg, ≥50.0 kg, unknown]
 
BMI (kg/m²)^{*1} [<18.5 kg/m², ≥18.5 kg/m² to <25.0 kg/m², ≥25.0 kg/m², unknown]
 
Disease to be treated/diagnosis [primary, secondary, unknown]
 
Duration of disease (years)^{*1} [<1 year, ≥1 year to <5 years, ≥5 years, unknown]
 
Predisposition to hypersensitivity [no, yes, unknown]
 
Presence or absence of concurrent illness^{*2} [no, yes, unknown]
 
Disposition of concurrent illness [locomotor/spine disease other than osteoporosis (spinal osteoarthritis, lumbago, spinal column stenosis, osteoarthritis, other), rheumatoid arthritis, lifestyle-related disease (diabetes, hypertension, dyslipidemia, chronic obstructive pulmonary disease, other), cardiac disease (angina pectoris, myocardial infarction, arrhythmia, other), renal disease (diabetic nephropathy, nephrotic syndrome, glomerulonephritis, other), hepatic disease (chronic hepatitis, hepatic cirrhosis, hepatic steatosis, other), digestive disease (esophageal ulcer, gastric ulcer, duodenal ulcer, esophagitis, other), other]
 
Presence or absence of medical history (except previous fracture)^{*2} [no, yes, unknown]
 
Disposition of medical history [cerebral infarction, myocardial infarction, thromboembolism, other]
 
Risk factors for fracture
 
Presence or absence of medical history (previous fracture)^{*2} [no, yes, unknown]
 
Disposition of medical history (previous fracture) [vertebra, femur, wrist, forearm, upper arm, pelvis, lower limb, other]
 
Previous steroid use (except topical preparations) [no, yes, unknown]
 
Disposition of previous steroid use [at least 3 months at a prednisolone
 |

- equivalent dose of 5 mg/day or more, otherwise, unknown dose]
 - Parental history of femur fracture [no, yes, unknown]
 - Drinking history (≥ 3 units per day) [no, yes, unknown]
 - Smoking history [never smoked, current smoker, past smoker, unknown]
 - Previous osteoporosis drug [no, yes]
 - Previous treatment group [Benet/Actonel (risedronate), bisphosphonate other than Benet/Actonel, calcium, vitamin D, osteoporosis drug not listed above (parathyroid hormone, anti-RANKL monoclonal antibody, other), steroid]
 - Presence or absence of concomitant medication [no, yes]
 - Disposition of concomitant medication [osteoporosis drug, anti-inflammatory analgesic, cardiovascular drug, central nervous system drug, antidiabetic, digestive system drug, other]
 - Combination therapy group [calcium, vitamin D, osteoporosis drug not listed above (parathyroid hormone, anti-RANKL monoclonal antibody, other), steroid]
 - Presence or absence of physical therapy [no, yes, unknown]
 - Presence or absence of other concomitant therapy (e.g., diet therapy, exercise therapy, block therapy) [no, yes, unknown]
 - Presence or absence of low back pain before the start of treatment [no, yes, unknown]
- 4) Analysis methods
- The number and proportion of patients will be calculated for the analysis item. Summary statistics will be calculated for analysis items with *1. Analysis items with *2 will be processed as specified in Section 5.1, “Handling of Dichotomous Variables.”

6.1.3. Treatment Compliance Status

- 1) Analysis set
- Patients evaluated for safety
- 2) Chart plan
- Table 1-3
- 3) Analysis item
- Treatment status [took the drug as instructed by a physician, took the drug on a different day from instructed by a physician, took no dose, unknown]
- 4) Analysis methods
- The number and proportion of patients will be calculated for the analysis item by the number of doses indicated by a physician. In addition, a stacked bar chart will be plotted with the percentage of number of patients on the vertical axis and the number of doses on the horizontal axis.

6.1.4. Changes in Dosing Interval over Time

- | | |
|---------------------|--|
| 1) Analysis set | Patients evaluated for safety |
| 2) Chart plan | Table 1-4 |
| 3) Analysis item | Dosing interval |
| 4) Analysis methods | Summary statistics will be calculated for the analysis item by the number of doses of Benet/Actonel. |

6.1.5. Number of Doses of Benet/Actonel

- | | |
|---------------------|---|
| 1) Analysis set | Patients evaluated for safety |
| 2) Chart plan | Table 1-5 |
| 3) Analysis item | Number of doses of Benet/Actonel [1-6 doses, 7-9 doses, 10-12 doses, 13-24 doses, 25-36 doses, ≥ 37 doses] |
| 4) Analysis methods | For the number of doses of Benet/Actonel, the number and proportion of patients in each category will be calculated, and summary statistics will be calculated. |

6.2. Analysis of Safety

The safety will be analyzed in patients evaluated for safety.

6.2.1. List of Occurrence of Adverse Drug Reactions/Infections in the Special Drug Use Surveillance (Attachment Style 2)

- | | |
|---------------------|--|
| 1) Analysis set | Patients evaluated for safety |
| 2) Chart plan | Table 2-1 |
| 3) Analysis items | Number of surveillance sites Number of surveyed patients Number of patients with an ADR, etc. Number of ADRs, etc. Proportion of patients with an ADR, etc. Proportion of patients with an ADR, etc. (number of ADRs, etc.) by type (SOC, PT) |
| 4) Analysis methods | The number and proportion of patients (number of events) will be calculated for the analysis item, and a list of occurrence of ADRs/infections will be prepared. |

6.2.2. List of Occurrence of Serious Adverse Events in Drug Use Surveillance/Special Drug Use Surveillance/Post-Marketing Clinical Study (Attachment Style 2-2, Attachment Style 10)

- 1) Analysis set Patients evaluated for safety
- 2) Chart plan Table 2-2
- 3) Analysis items Number of surveillance sites
Number of surveyed patients
Number of patients with a SAE
Number of SAEs
Proportion of patients with a SAE
Proportion of patients with a SAE (number of SAEs) by type (SOC, PT)
- 4) Analysis methods The number and proportion of patients (number of events) will be calculated for the analysis item, and a list of occurrence of SAEs will be prepared.

6.2.3. Occurrence of Adverse Drug Reactions by Type

- 1) Analysis set Patients evaluated for safety
- 2) Chart plan Table 2-3
- 3) Analysis item ADR type (SOC, PT)
- 4) Classification factors Seriousness [serious, not serious]
Time of onset [Days 1-7, Days 8-14, Days 15-21, Days 22-28, Days 29-56, Days 57-84, Days 85-180, Days 181-210, Days 211-360, Day 361 or later, unknown]
Outcome [recovered, recovering, not recovered, recovered with sequelae, death, unknown]
- 5) Analysis methods The number of ADRs by PT will be calculated for each category of classification. The number of patients with an ADR by SOC will be calculated only as the total.

6.2.4. List of Occurrence of Adverse Drug Reactions in Patients Not Evaluated for Safety

- 1) Analysis set Patients not evaluated for safety
- 2) Chart plan Table 2-4
- 3) Analysis items Number of surveillance sites
Number of surveyed patients
Number of patients with an ADR, etc.
Number of ADRs, etc.
Proportion of patients with an ADR, etc.

| | |
|---------------------|---|
| | Proportion of patients with an ADR, etc. (number of ADRs, etc.) by type (SOC, PT) |
| 4) Analysis methods | The number and proportion of patients (number of events) will be calculated for the analysis item, and a list of occurrence of ADRs will be prepared. |

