10.4 Matters on Safety

For the safety population, the incidence of AEs reported during the observation period will be tabulated by causal relationship to Benet, type, seriousness, and time of onset.

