3.2. Definitions of Terms

| Term | Description |
|-----------------------------|--|
| Finalized patient | For Benet Tablets, a finalized patient is defined as a patient who has the date of CRF approval in the PMS system. For Actonel Tablets, a finalized patient is defined as a patient who has the date of temporary finalization in the business management system. |
| Adverse event (AE) | All events entered into the column of [Adverse event] or [Assessment of non-vertebral fracture] in the case report form (CRF) Any unfavorable or unintended sign (e.g., abnormal laboratory finding), symptom, or disease temporally associated with the use of Benet/Actonel, whether or not it is considered related to Benet/Actonel |
| Adverse drug reaction (ADR) | All adverse events except those not related to Benet/Actonel according to “Causal relationship to Benet/Actonel” both in the column of [Adverse event] or [Assessment of non-vertebral fracture] in the CRF and determined by the company If either assessment is missing, non-missing assessment of causal relationship is confirmed to determine the adverse event as an adverse drug reaction unless not related to Benet/Actonel. |
| Serious adverse event (SAE) | Adverse event assessed as serious according to “Seriousness” at least either in the column of [Adverse event] or [Assessment of non-vertebral fracture] in the CRF or determined by the company, including “AEs that must always be assessed as serious” in the implementation guidelines and AEs in Takeda Medically Significant AE List |

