5.2. Handling of Adverse Events

Multiple episodes of the same AE/ADR (SOC) in the same patient will be tabulated as 1 patient.

Multiple episodes of the same AE/ADR (PT) in the same patient will be tabulated as 1 event.

For tabulation by type (seriousness, time of onset, outcome), multiple episodes of the same AE/ADR (PT) in the same patient will be tabulated as 1 event on a PT basis according to the following order of precedence:

Seriousness: serious > not serious

Time of onset: chronological order

Outcome: death > recovered with sequelae > not recovered > recovering > recovered > unknown

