| Flag for employment of data | It is identified whether measurement data are employed. |
| Flag for event | A patient with event is defined as a patient who experienced at least one event such as vertebral fracture. A patient with no event is defined as a patient who experienced no event. |
| Time point of event onset | Time point of event onset is defined as the first onset of event such as vertebral fracture. Patients with no event are censored at the final assessment. |
| Measured value before the start of treatment | The measured value before the start of treatment is identified. |
| Change | Value obtained by deducting the measured value before the start of treatment from a measured value at each time point |
| Percent change (%) | Value obtained by dividing a change by the measured value before the start of treatment and then multiplying the division by 100 |
| Time of onset (days) | Number of days from the start date of Benet/Actonel treatment to the date of onset of AE “Date of onset” - “start date of Benet/Actonel treatment” + 1 |
| Flag for inclusion/exclusion as an AE | It is identified whether an event is an AE. |
| Relationship (for analysis) | It is identified whether an AE is related to Benet/Actonel. The causal relationship is handled as specified for “Adverse drug reaction” in Section 3.2. |
| Seriousness (for analysis) | It is identified whether an AE is serious. The seriousness is |

| Derived variable | Description |
|-------------------------------|--|
| | handled as specified for “Serious adverse event” in Section 3.2. |
| Novelty | It is identified whether an AE is expected (known) or unexpected (unknown) based on the precautions for Benet/Actonel. |
| Presence or absence of an AE | It is identified whether there is an AE (including “unknown”). |
| Presence or absence of an ADR | It is identified whether there is an ADR (including “unknown”). |
| Presence or absence of a SAE | It is identified whether there is a SAE (including “unknown”). |

6. Analysis Plan

Analysis sets, analysis items, and analysis methods are shown below. Details of variables for analysis and display will be specified in separately prepared statistical analysis specifications.

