6.4. Listing

6.4.1. List of Discontinued Patients

- | | |
|-----------------|-----------------------|
| 1) Analysis set | Discontinued patients |
|-----------------|-----------------------|

| | |
|---------------------|---|
| 2) Chart plan | Table 4-1 |
| 3) Analysis items | Patient number, sex, age, included in or excluded from the analysis set, start date and discontinuation date of Benet/Actonel treatment, number of days from start to discontinuation of Benet/Actonel treatment, reason for discontinuation, presence or absence of an AE, AE term |
| 4) Analysis methods | A list with the analysis items will be prepared. |

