6.4.2. List of Patients Not Evaluated

| | |
|---------------------|---|
| 1) Analysis set | Patients not evaluated for safety Patients not evaluated for efficacy Patients not evaluated for vertebral fracture |
| 2) Chart plan | Table 4-2 |
| 3) Analysis items | Patient number, sex, age, included in or excluded from the analysis set, start date of Benet/Actonel treatment, reason for exclusion, presence or absence of an AE, AE term |
| 4) Analysis methods | A list with the analysis items will be prepared. |

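### Protocol 10.4 promises the incidence of all adverse events by relationship, type, seriousness and onset, but SAP 5.1 plans safety incidence tables only for adverse drug reactions and serious adverse events

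*SAP*

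**What the plan says.** Protocol 10.4, which concerns the safety population, states that "the incidence of AEs reported during the observation period will be tabulated by causal relationship to Benet, type, seriousness, and time of onset". The sentence is the same in every protocol version in the file.

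SAP 5.1 section 6.2 plans four safety outputs:

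- Table 2-1 (6.2.1): ADRs/infections, number and proportion of patients by SOC and PT.
- Table 2-2 (6.2.2): serious AEs, number and proportion of patients by SOC and PT.
- Table 2-3 (6.2.3): ADRs by seriousness, time of onset and outcome. Here "The number of ADRs by PT will be calculated for each category of classification"; patient counts by SOC are given only as a total.
- Table 2-4 (6.2.4): ADRs in patients not evaluated for safety.

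SAP 3.2 defines an ADR by exclusion: "All adverse events except those not related to Benet/Actonel according to" both the case report form (CRF) and the company's assessment. If one assessment is missing, the other decides. SAP 5.2 sets the counting rule for AEs and ADRs alike: "Multiple episodes of the same AE/ADR (PT) in the same patient will be tabulated as 1 event".

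AE terms also appear in two listings. Table 4-1, for discontinued patients, includes "reason for discontinuation, presence or absence of an AE, AE term". Table 4-2, for patients not evaluated for safety, efficacy or vertebral fracture, includes "reason for exclusion, presence or absence of an AE, AE term". Table 4-3, for all patients with a collected CRF, carries ADRs only.

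**The concern.** A split by causal relationship has meaning only if events on both sides of it are counted, so 10.4 cannot be read as a promise about ADRs alone. Protocol 13.1 uses the term ADR where it means ADR. An analyst who follows SAP 5.1 exactly will not produce the result that 10.4 describes.

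This matters because the surveillance has no comparator and pools the two brands (protocol 10.0). Whether an event counts as drug-related rests on the judgement of the site and the company. A reader can weigh that judgement only if the events judged not related are shown beside the others. The protocol collects what is needed: section 9.3 asks for the rationale behind each not-related assessment and names event groups that must go into the AE column.

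**Working it through.** No arithmetic from the plan has to be reproduced. The check sets the 10.4 promise against every planned output in SAP 5.1.

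**1. Who falls outside the ADR definition.** Under SAP 3.2, events with an unevaluable relationship remain ADRs. Only AEs judged not related by both site and company, or by the one assessment available, fall outside.

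**2. Are the ADR counts usable as incidence?** Yes. With one event per PT per patient (SAP 5.2), the PT counts in Table 2-3 are counts of patients, so type, seriousness and onset are covered for ADRs.

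**3. Coverage of the four groups in patients evaluated for safety.**

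| Group | Incidence by SOC/PT | Time of onset |
|---|---|---|
| ADR, serious | Tables 2-1, 2-2, 2-3 | Table 2-3 |
| ADR, non-serious | Tables 2-1, 2-3 | Table 2-3 |
| Not related, serious | Table 2-2 | none |
| Not related, non-serious | none | none |

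Incidence is planned for 3 of 4 groups. Onset is planned for ADRs only, and as one group: SAP 6.2.3 does not say that onset is crossed with seriousness. No table uses relationship as a classification factor, and none gives the overall incidence of AEs.

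**4. Can the split be recovered for serious AEs?** In part. For a given PT, patients in Table 2-2 minus patients with a serious ADR in Table 2-3 gives the patients whose serious AE of that PT was never classed as an ADR. A patient with both a related and an unrelated serious episode of the same PT is hidden. The differences cannot be summed to a patient total, because one patient may contribute several PTs. Onset cannot be recovered at all.

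**5. Do other sections fill the gap?**

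- Section 6.1 has no AE output.
- Section 6.3 counts vertebral and non-vertebral fractures whatever their causality, but as efficacy events in efficacy sets.
- Tables 4-1 and 4-2 print AE terms whatever their causality or seriousness, but only for their own patients. They carry no relationship, seriousness, AE onset or incidence.

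**6. Events named in protocol 9.3.** Eight groups are listed for the AE column. One, atypical femur fracture, falls under SAP 6.3.2. For the other seven (8 − 1 = 7), such as upper gastrointestinal disorder, musculoskeletal pain and atrial fibrillation, a case classed as non-serious and not related reaches no safety incidence table.

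**The case against.** The strongest defence is that the narrowing is deliberate. The amendment history says version 5.0 was revised for the re-examination and 5.1 for a serious AE list, and several tables follow named attachment formats. That is plausible, and it bears on which remedy to choose. It does not remove the conflict, because neither document states the restriction and 10.4 was left unchanged.

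A second defence is that the separate chart plan or analysis specifications may hold the missing table. The SAP gives those documents layout and details of variables and display, and says that the analysis sets, items and methods are set out in its own section 6.

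Some stronger readings that a reader might infer are not supported:

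- *That unrelated, non-serious AEs vanish from all output.* They do not. Tables 4-1 and 4-2 print their terms for some patients, and fractures are tabulated in 6.3.
- *That the relationship of serious AEs is wholly lost.* It can be partly inferred by PT, as shown above.
- *That the gap can be sized from the dropout rate in protocol 3.2.* That would count patients outside a listing, not AEs missing from an incidence table. Even a complete listing would not supply the incidence.
- *That every unrelated case in the seven non-fracture groups is affected.* SAP 3.2 also counts as serious the events on an always-serious list in the implementation guidelines, which are not among the documents. Cases on that list would reach Table 2-2.

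**Conclusion.** The inconsistency between protocol and SAP stands. Fractures apart, AEs that are both non-serious and judged not related enter no safety incidence table. Serious AEs judged not related have no onset tabulation. Overall AE incidence and a related/unrelated split of all AEs are not planned.

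The size can be stated only as coverage: incidence for three of four groups, and onset for ADRs alone. The documents give no AE rate from which to count events. The conclusion assumes that the supplied SAP is the full list of planned analyses, and that the word infections in the title of Table 2-1, which the SAP does not define, does not bring in infections judged unrelated.

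The primary endpoint and the efficacy results are unaffected. This should be corrected, but it is a gap in safety reporting and does not invalidate the design.

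**What to change.** Add one table in patients evaluated for safety: number and proportion of patients with any AE, overall and by SOC and PT, split by relationship, seriousness and time of onset. SAP 5.5 already derives all three for AEs; for the relationship variable it says "It is identified whether an AE is related to Benet/Actonel". State whether the splits are crossed, because the onset of serious AEs judged not related can be read only if they are.

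Add one line to the precedence rules in SAP 5.2, which now cover seriousness, onset and outcome: *Relationship: related (ADR) > not related*.

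The cost is one extra table and one line of text, with no new data collection. Superseded SAP 3.0 had a table with these dimensions (its Table 2-3, counts only, so proportions would be added). It is cited to show feasibility; its later removal is not in itself an error.

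If output limited to ADRs and serious AEs is intended, the alternative is to state and justify the departure in the SAP, or to revise protocol 10.4 to match.

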6.3. Analysis of Efficacy

The efficacy will be analyzed in patients evaluated for efficacy. Patients with no pre- or post-baseline data on the relevant efficacy endpoint will be excluded from analysis.

6.3.1. Incidence of Vertebral Fracture

| | |
|---------------------|--|
| 1) Analysis set | Patients evaluated for efficacy with dates of pre- and post-treatment ^{*1} radiography Patients evaluated for vertebral fracture |
| 2) Chart plan | Table 3-1-1-1 Table 3-1-1-2 Table 3-1-1-3 Table 3-1-1-4 Table 3-1-1-5 Table 3-1-1-6 Table 3-1-2-1 Table 3-1-2-2 Table 3-1-2-3 Table 3-1-2-4 Table 3-1-2-5 Table 3-1-2-6 |
| 3) Analysis items | New vertebral fracture or worsening of prevalent fracture New vertebral fracture or worsening of prevalent fracture <non-traumatic> New vertebral fracture New vertebral fracture <non-traumatic> Worsening of prevalent fracture Worsening of prevalent fracture <non-traumatic> |
| 4) Analysis methods | For the time to the first onset of the analysis item, the point estimate of cumulative incidence, standard error, and 95% confidence interval will be calculated using the Kaplan-Meier method, and the number of relevant patients (number of patients at risk), cumulative number of patients with |

the analysis item, and cumulative number of censored patients at Month 6 (Day 180), Month 12 (Day 360), Month 18 (Day 540), Month 24 (Day 720), Month 30 (Day 900), and Month 36 (Day 1096) will be calculated. In addition, a Kaplan-Meier curve will be plotted with the cumulative incidence (%) on the vertical axis and the time (months) on the horizontal axis. The number of relevant patients (number of patients at risk) will be presented under the time (months).

The time to the first onset of the analysis item is defined as time from the start date of Benet/Actonel treatment to the earliest date of radiography with a diagnosis of the analysis item. Patients with no analysis item will be censored at the latest date of radiography with no evidence of the analysis item.^{*2}

No radiographic data collected after the end date of Benet/Actonel treatment + 90 days or after 3 consecutive months (90 days) of interruption in patients with interruption of treatment will be used for analysis.

*1 Range of assessment before and after treatment

- Before treatment: before the start of Benet/Actonel treatment defined as Days -90 to 1
- After treatment: before the end date of Benet/Actonel treatment + 90 days, and before 3 consecutive months (90 days) of interruption in patients with interruption of treatment

*2 The date of radiography with no evidence of the analysis item is defined as follows for each analysis set:

- Patients evaluated for efficacy with dates of pre- and post-treatment radiography: date when it is determined that the analysis item has not occurred
- Patients evaluated for vertebral fracture: date when it is determined that the analysis item has not occurred and radiography is performed on the same location (thoracic spine, lumbar spine) as before treatment (before the start of Benet/Actonel treatment defined as Days -90 to 1) (for instance, the day of lumbar spine radiography will not be handled as the date when it is determined that the analysis item has not occurred for patients with thoracic spine radiography before

treatment.)

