9.2.5 Assessment of Vertebral Fracture

1) Surveillance items

Vertebral fracture before the start of Benet treatment (baseline) will be confirmed, and the date of radiography, radiographic location, and location of vertebral fracture will be entered into the CRF. Then, the presence or absence and location of new vertebral fracture, presence or absence of worsening of prevalent vertebral fracture, and presence or absence of apparent trauma during treatment and at the end of the observation period (or discontinuation of treatment) relative to baseline will be entered into the CRF.

2) Time points of surveillance

At the start of Benet treatment, 12, 24, and 36 months after the start of treatment (or discontinuation of treatment), and when vertebral fracture is suspected during the observation period

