4.4. Patients Evaluated for Efficacy

All patients evaluated for safety, excluding those who meet the following criterion:

Pre- and post-baseline values of all efficacy endpoints (bone turnover markers, bone mineral density, vertebral fracture, non-vertebral fracture, height, and low back pain) are unknown, including incalculable values

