4.5. Patients Evaluated for Vertebral Fracture

All patients evaluated for efficacy, excluding those who meet any of the following criteria:

1) No evidence of 1 to 4 fractures from the fourth thoracic vertebra to the fourth lumbar vertebra provided by thoracic and lumbar spinal radiography performed before the start of the surveillance^{*}

* The permissible range before the start of the surveillance is Days -90 to 1.

2) Not 50 years or older

3) Not an outpatient who can walk

4) No known date of pre- or post-treatment^{*} radiography for assessment of vertebral fracture

* For the permissible range before or after treatment, refer to *1 in Section 6.3.1.

5. Handling of Data

Handling of data for analysis is described below. Details of processing will be specified in separately prepared analysis data set specifications.

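### SAP 6.3.1: in the broader film set, the two worsening curves can include patients with no baseline vertebral fracture, which would scale the estimate by about (1 − f)

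*SAP*

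**What the plan says.** All SAP references are to version 5.1.

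- **Two sets, six items.** Section 6.3.1 names two analysis sets, six vertebral items and twelve tables, so each item is run in each set. The last two items are "Worsening of prevalent fracture Worsening of prevalent fracture <non-traumatic>". The first set is "Patients evaluated for efficacy with dates of pre- and post-treatment" radiography; the second is the set defined in section 4.5.
- **Parent of the first set.** Section 4.4 starts from "All patients evaluated for safety, excluding those who meet the following criterion". The single criterion is that "Pre- and post-baseline values of all efficacy endpoints (bone turnover markers, bone mineral density, vertebral fracture, non-vertebral fracture, height, and low back pain) are unknown". Baseline fracture status plays no part.
- **Where baseline fracture is required.** Only section 4.5 has the condition. Its first exclusion is "No evidence of 1 to 4 fractures from the fourth thoracic vertebra to the fourth lumbar vertebra".
- **Estimator and censoring.** Cumulative incidence is "calculated using the Kaplan-Meier method", with the number at risk printed. Patients without the event are censored at the latest film negative for the item, which for the first set means: "Patients evaluated for efficacy with dates of pre- and post-treatment radiography: date when it is determined that the analysis item has not occurred".
- **What is recorded.** Protocol section 9.2.5 collects the location of baseline vertebral fractures and, relative to baseline, the "presence or absence of worsening of prevalent vertebral fracture".

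No sentence in 6.3.1 limits the worsening items to patients who have a prevalent fracture.

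**The concern.** Worsening is defined against a fracture that is already there. A patient whose baseline spine is fracture-free has nothing that can worsen and is not at risk at any time. Such a patient meets the written definition of the first set, contributes no events to the two worsening curves, and adds to the number at risk until the last negative film.

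The resulting figure would no longer be the incidence of worsening among patients with a prevalent fracture. It would be that incidence averaged with a group at zero risk, with the group's size unstated. The other items do not share the problem: a patient with a normal spine can have a new fracture, and so can have the combined event. Section 6.3.3 is run only in the 4.5 set, so it is not touched either.

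**Working it through.** **The plan's own figures.** The documents state no incidence of worsening, so there is no plan figure to reproduce on this item. The one related design figure does reproduce: Protocol 3.2 wants about 250 analysable patients with 50% dropout, and 250 / (1 − 0.50) = 500. It serves below only as a scale for precision.

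**Step 1: who is in the first set but not the second.** Criterion 4 of section 4.5 asks for known film dates before and after treatment and points to the window in note *1 of 6.3.1. The first set already applies that requirement. The first set therefore adds only patients with dated films who fail criteria 1 to 3 of 4.5: those without 1 to 4 fractures in T4 to L4, those under 50, and those who are not ambulatory outpatients. Criterion 1 covers patients with no fracture, but also those with more than four or with fractures only outside T4 to L4. Only patients with no vertebral fracture at all are outside the risk of worsening.

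**Step 2: whether another rule removes them.** Section 6.3 drops patients with no data before or after baseline on the relevant endpoint. A dated film showing no fracture is data, so on its natural reading this rule does not remove them.

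**Step 3: effect on the estimate.** Let F(t) be the cumulative incidence of worsening among patients with a prevalent fracture, and f the share of the set with none. If censoring is the same in both groups, Kaplan-Meier estimates the mixture:

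- survival in the mixture = f × 1 + (1 − f) × (1 − F(t))
- cumulative incidence in the mixture = (1 − f) × F(t)

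The relative understatement equals f.

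**Step 4: numbers.** Neither f nor F is in the documents. Both are assumptions: f from 0% to 30%, and F at 36 months of 5%, 10% or 20%.

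| f | F = 5% | F = 10% | F = 20% |
|---|---|---|---|
| 0% | 5.00% | 10.0% | 20.0% |
| 2% | 4.90% | 9.8% | 19.6% |
| 5% | 4.75% | 9.5% | 19.0% |
| 10% | 4.50% | 9.0% | 18.0% |
| 20% | 4.00% | 8.0% | 16.0% |
| 30% | 3.50% | 7.0% | 14.0% |

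**Step 5: check by simulation.** Assumptions: true F = 10% at 36 months, yearly films, about 50% dropout over three years, 200 runs of 2,000 patients. Here f is the share before a post-treatment film is required.

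| f | Equal dropout | Patients without a fracture drop out at twice the rate |
|---|---|---|
| 5% | 9.50% | 9.60% |
| 10% | 9.05% | 9.43% |
| 20% | 8.05% | 8.60% |
| 30% | 7.09% | 7.87% |

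Restricting the same data to patients with a prevalent fracture gave 9.9% to 10.1% throughout. Unequal dropout of this kind makes the bias smaller but leaves it downward.

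**Step 6: scale.** With 250 patients and 10% incidence, a simple standard error is √(0.10 × 0.90 / 250) = 1.90 points, and the 95% interval is 10% ± 3.7 points, or 6.3% to 13.7%. A shift of 0.5 to 1 point (f of 5% to 10%) lies well inside it.

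**The case against.** The best counter-argument is that there may be no such patients. Protocol section 4.0 requires 1 to 4 fractures in T4 to L4 at entry, the registration form records the assessment against the selection criteria, and section 7.3 has the registration center turn away ineligible patients. The open-ended last item of SAP 4.3 might also remove those who slipped through, if the selection criteria count as registration criteria. The first part stands: f may be near zero. The second is doubtful, because the SAP does not say so and criteria 1 to 3 of section 4.5 would then have little left to do.

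A reader might infer from criterion 1 of 4.5 that the sponsor expects patients with a normal spine. The text does not support that. The criterion repeats the entry rule, may be precautionary, and also catches patients with too many fractures or with fractures only elsewhere in the spine.

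The censoring step also depends on coding. If worsening is left blank or marked not applicable for a patient without a prevalent fracture, the separate data specifications might drop that patient. Protocol 9.2.5 asks for presence or absence, which makes a recorded absence the likelier outcome, but the documents do not settle it.

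Finally, the same two items are run in the 4.5 set, so an estimate free of this problem is already planned. Sections 6.1.1 and 6.4.2 also report exclusions from that set with reasons, which helps a reader bound f. That limits the harm. It does not correct the first-set curves, and a reason that merely cites criterion 1 would not separate no fractures from more than four.

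**Conclusion.** The gap is real and its effect is conditional. As written, the first set's two worsening curves can include patients who cannot have the event, and any such patients lower the estimate by a factor of about (1 − f). This rests on similar follow-up in the two groups and on these patients being recorded as free of worsening. For an assumed true 10%, the reading is 9.5% at f = 5% and 9% at f = 10%; at f = 0 nothing changes. The higher values of f in the tables show the range only and have no support in the documents.

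A reader might go on to infer that the first set will show less worsening than the second, and that this would flatter the drug in routine practice. That does not follow. The first set also adds patients with more than four fractures, who have more vertebrae that can worsen. The two sets also censor differently, because only the second requires a negative film of the same spinal region as at baseline. The direction of any difference between the sets is open.

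The items concerned are descriptive components of the vertebral fracture analysis, with no test or decision attached. The matter is a correctable flaw in one denominator and does not threaten the primary result.

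**What to change.** Add one sentence to SAP 6.3.1: *In the first analysis set, the two worsening items are analysed only in patients with at least one vertebral fracture on the baseline film (Days −90 to 1), and the number of patients excluded for this reason is reported.* Leave the new-fracture and combined items, and everything in the second set, as they are.

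This condition keeps patients with more than four fractures, who are at risk. Reporting the number excluded gives f directly and shows whether the issue ever mattered.

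The cost is one filter on baseline fracture location, which the case report form already collects, and a slightly smaller denominator for these two items. If no patient lacks a baseline fracture, the results are identical.
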